## 5.0 GENERAL CONSIDERATIONS FOR STATISTICAL ANALYSIS

Data on continuous scale will be expressed as mean, standard deviation, standard error, median, 95%CI and number of patients in each treatment group. Categorical type of data will be presented with frequency and the percentages of patients in each treatment group. Statistical Analysis. Software (i.e. SAS® 9.4 or higher) will be used to perform all analyses.

### 5.1 Sample Size Determination

AUR101 doses will be tested versus placebo with respect to the primary endpoint (PASI 75 response). A sample size of 25 in each of the three arms will provide an 80% power with a one-sided Type I error of 0.05, if the true placebo response rate is 7% and the response rate on investigational arm(s) is 35%. The sample size is increased to 30 to account for ~ 15-20% dropouts over the study period. Placebo response rates from previous studies was 4-7% in most of the studies in similar patient population. No multiplicity adjustments were considered in the sample size calculation as it is a POC study.

A subset of approximately 25 consenting patients will participate in the pharmacokinetic part in addition to main study.

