11.0 DATA MANAGEMENT AND STATISTICAL ANALYSIS

11.1 Sample Size Calculation

AUR101 doses will be tested versus placebo with respect to the primary endpoint (PASI75 response). A sample size of 25 in each of the three arms will provide an 80% power with a one-sided Type I error of 0.05, if the true placebo response rate is 7% and the response rate on investigational arm(s) is 35%. The sample size is increased to 30 to account for \sim 15-20% drop outs over the study period.

Placebo response rates from previous studies was 4-7% in most of the studies in similar patient population [17-19].

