11.5 Efficacy Analysis

Summary statistics with 95% confidence interval will be presented for PASI, IGA DLQI scores. PASI 75, PASI 50 responses, IGA responders (patients achieving IGA 0 or 1) will be summarized by treatment groups. Change from baseline in DLQI scores will be summarized by the treatment groups. Appropriate parametric or non-parametric tests will be applied to test the significance between active arms vs. placebo. No multiplicity adjustments will be done.

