#### 4.3.4 Efficacy population

Efficacy population will include patients who

- have a valid baseline and at least one post-baseline (follow up) assessment for
- PASI score by the independent dermatologist or withdrawal is associated with lack of effect by the patient before post-baseline assessment.
- do not have any major protocol or inclusion/exclusion violations,

Efficacy population will provide sample for analysis of primary, secondary and exploratory endpoints. For patients who dropped out during study treatment period due to any reason, data from the last efficacy assessment will be considered for the primary endpoint and other secondary efficacy endpoints relevant at other future time-points as per Last Observation Carried Forward (LOCF) approach.

Efficacy data collected solely based on the photographs without on-site examination by the investigator/independent dermatologist will not be considered for the analysis and this data will also be imputed with LOCF approach.

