## 6.0 GENERAL CONSIDERATIONS FOR STATISTICAL ANALYSIS

The statistical analysis will be performed using the SAS version 9.4. The descriptive statistics for the continuous data will be presented using mean, standard deviation, standard error, median and 95% CI, whereas, for the categorical data it will be presented using number of observations (n) and percentages (%) For continuous data, normality will be tested though “Kolmogorov-Smirnov Goodness-of-Fit Test”. If normality assumption will not fulfil then non-parametric methods such as Mann Whitney U/ Kruskal Wallis Test will be used.

Following statistical tests/procedure will be performed wherever required:

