## 7.0 EFFICACY ANALYSES

### 7.1 Primary Efficacy Analysis

Summary statistics with 95% confidence interval will be presented for PASI. Comparison of percentage of patients achieving at least 75% reduction from Baseline

	JSS Medical Research India Private Limited Data Management		
Title: Statistical Analysis Plan-Module I			
SOP Number: JSS-DM-BIS-01	Current Version Number: 1.0	Previous Version Number: Nil	Document Date: 25MAR2021

PASI score (PASI-75) to Week 12 between treatment arm and placebo will be evaluated using Chi-square/Fisher's exact test with responder and non-responder psoriasis type. Also, 95% CI for the responders within treatment will be evaluated by using Clopper-Pearson method and 95% CI for treatment difference will be evaluated by using Miettinen-Nurminen method.

Additional sensitivity analysis will be tested by using Cochran-Mantel-Haenszel (CMH) test after adjusting the sites and baseline PASI score. The analysis will be performed on efficacy population. No multiplicity adjustments will be done for the primary analysis.

Two sets hypotheses will be tested,

1.  $H_0: P_1=P_0$  vs  $H_1: P_1 \neq P_0$
2.  $H_0: P_2=P_0$  vs  $H_1: P_2 \neq P_0$

Where,  $P_0$ ,  $P_1$  and  $P_2$  are the proportion of responders in placebo, 400 mg and 600 mg arms, respectively. Since, both hypotheses will be tested separately, no multiplicity adjustment will be done.

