**Title: Statistical Analysis Plan-Module I**

 SOP Number:  
 JSS-DM-BIS-01

Current Version Number: 1.0

Previous Version Number: Nil

 Document Date:  
 25MAR2021

?

Summary descriptive statistics will consist of the number and percentage of responses in each category for discrete variables, and the mean, median, standard deviation (SD), SE, median and 95% confidence interval for continuous variables.

Mean and Median values will be reported to one decimal place. Standard deviation, standard error and 95% confidence interval values will be reported to two decimal places.

Percentages will be rounded to one decimal place. Where appropriate, the number and percentage of responses will be presented in the form XX (XX.X %).

All Adverse Events (AE) and Serious Adverse Events (SAE) will be presented: Number of events, Number of subjects and %(n/N) of subjects.

P-values will be rounded to three decimal places. P-values less than 0.001 will be reported as <0.001 in tables. P-values greater than 0.999 will be reported as >0.999.

P value <0.05 will be considered significant.

All listings will be sorted for presentation in order of site number, patient number, date of procedure or event.

All categories of variables will be presented even if there is no data. Zero frequencies are going to be represented as “0 (0.0%)” in reporting of results.

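### The 80% power is for a one-sided 0.05 test; the SAP tests two-sided at 0.05 and leaves chi-square or Fisher open, so power per dose is about 74% or 60% at 25 per arm and 80% or 69% at 30

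*SAP*

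**What the plan says.** Protocol 11.1 and SAP 5.1 give the same sample size statement. In the SAP it reads "A sample size of 25 in each of the three arms will provide an 80% power with a one-sided Type I error of 0.05", with true PASI 75 rates of 7% on placebo and 35% on active. Each arm is then raised to 30 for 15-20% dropout.

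SAP 7.1 sets two primary hypotheses, one per dose against placebo, each with a not-equal alternative and no multiplicity adjustment. The comparison "will be evaluated using Chi-square/Fisher's exact test", and the "95% CI for treatment difference will be evaluated by using Miettinen-Nurminen method". SAP 9.1 adds "P value <0.05 will be considered significant".

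Neither document says when chi-square gives way to Fisher. SAP 6.0 (general considerations) gives code for both under "Following statistical tests/procedure will be performed wherever required". Protocol 11.5 says "Appropriate parametric or non-parametric tests will be applied to test the significance between active arms vs. placebo".

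On how many patients are analysed, SAP 4.3.4 says "For patients who dropped out during study treatment period due to any reason, data from the last efficacy assessment will be considered". Most dropouts therefore stay in by LOCF. Patients with major violations are excluded, as are those with no post-baseline PASI unless they withdrew early for lack of effect.

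**The concern.** The sample size section and the analysis section describe different tests. A not-equal alternative judged at p<0.05 is a two-sided 0.05 test, although the SAP never uses the word two-sided. No section states a one-sided primary analysis or a two-sided 0.10 threshold. The quoted power therefore belongs to a test the SAP does not run.

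The test it does run is also not fixed. With few placebo responders expected, chi-square and Fisher differ right where the decision falls. If the choice is made after the data are seen, it can determine whether a dose is declared effective. A Fisher p-value above 0.05 could also stand beside a confidence interval that excludes zero. SAP 1.0 foresees use of the results for sample size amendment, publications and regulatory submissions, so the ambiguity would reach outside readers.

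**Working it through.** **Inputs.** Rates p0 = 0.07 and p1 = 0.35, one-sided 0.05, n = 25 raised to 30 per arm (protocol 11.1, SAP 5.1). Not-equal alternatives and chi-square/Fisher (SAP 7.1). Threshold p<0.05 (SAP 9.1).

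**1. The plan's own figure.** Normal approximation with pooled variance under the null: power = Φ[(d − z·SE0)/SE1], where
- d = 0.35 − 0.07 = 0.28
- SE0 = √(2 × 0.21 × 0.79/25) = 0.1152
- SE1 = √((0.07 × 0.93 + 0.35 × 0.65)/25) = 0.1082

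One-sided, z = 1.645: (0.28 − 0.1895)/0.1082 = 0.837, so power is 79.9%. The stated 80% is right for its own inputs.

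**2. Same formula, two-sided.** With z = 1.960: (0.28 − 0.2258)/0.1082 = 0.501, so power is 69.2% at 25 per arm. At 30 per arm it is 77.3%. This formula needs 33 per arm for 80%.

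**3. Exact power of the planned tests.** For every pair of responder counts (x on placebo, y on active), the binomial probabilities at 0.07 and 0.35 are multiplied, then summed over the tables with two-sided p<0.05.

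| Two-sided p<0.05 | 25 per arm | 30 per arm |
|---|---|---|
| Pearson, no continuity correction | 73.8% | 79.8% |
| Fisher's exact | 59.7% | 69.2% |
| Fisher only if an expected count is below 5 (assumed rule) | 69.8% | 77.0% |
| Chi-square significant, Fisher not | 14.1% | 10.6% |
| Fisher significant, chi-square not | 0% | 0% |
| Some expected count below 5 | 36% | 15% |

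Like for like, the exact one-sided Pearson power at 25 per arm is 82.9%. Moving to two-sided therefore costs about 9 points exactly (82.9% to 73.8%) and about 11 by the normal formula (79.9% to 69.2%).

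**4. Where the tests part.** With 2 placebo responders, Pearson needs 8 active responders and Fisher needs 9, at either sample size. With 1 placebo responder out of 30, Pearson needs 6 and Fisher needs 8.

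Example, 8/30 against 2/30:
- Pooled rate 10/60, SE = √(2 × (1/6) × (5/6)/30) = 0.0962, z = 0.20/0.0962 = 2.08
- Pearson p = 0.038; Fisher p = 0.080
- Miettinen-Nurminen 95% CI 1.1% to 39.2%, which excludes 0

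**5. Exact type I error (two-sided).**

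| | 25 per arm | 30 per arm |
|---|---|---|
| Pearson, common rate 7% | 3.5% | 4.4% |
| Pearson, maximum over rates | 6.5% | 5.5% |
| Fisher, common rate 7% | 0.3% | 0.4% |
| Fisher, maximum over rates | 3.3% | 2.7% |

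**The case against.** The strongest reply is that the loss may be small. LOCF keeps most dropouts, so the analysed number should lie nearer 30 than 25, and at 30 the uncorrected chi-square has 79.8% power, essentially what was promised. This is correct as arithmetic. It requires that nobody is excluded, that the uncorrected chi-square is the test used, and that the 35% and 7% rates survive LOCF, which the documents do not quantify. The plan itself budgets on 25.

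A second reply is that naming the two tests together is common shorthand for chi-square with Fisher when expected counts are small. On that reading power is 69.8% or 77.0%, and the 8/30 against 2/30 example, whose smallest expected count is exactly 5, would go to chi-square. That reading is plausible, but the SAP does not state it, and power still falls short of 80%. Fisher throughout is the low end of the range, not the expected case.

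Third, the placebo rate matters more than sidedness. At 4%, the low end in SAP 5.1, two-sided chi-square power is 86.7% (25 per arm) or 91.6% (30). At 10%, the upper end in protocol 3.4.2, it is 60.1% or 66.1%. This is a fair caution against over-reading the decimals, but it does not reconcile the two sections.

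Finally, this is a proof-of-concept trial. If both doses reach 35%, the chance that at least one is significant by chi-square is 87.6% (25) or 91.5% (30). A one-sided test could also be defended in that setting, but SAP 7.1 and 9.1 would then have to say so.

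**Conclusion.** The concern holds. The stated power is correct for a one-sided 0.05 test and wrong for the test the SAP specifies. At 25 analysed per arm, a dose with the planned effect would be missed in about 26% of trials (chi-square) or 40% (Fisher), against the stated 20%. At 30 the figures are 20% or 31%. The effect therefore runs from negligible (all 30 analysed, chi-square) to material (25 analysed, Fisher). Separately, the unspecified choice of test would change the primary conclusion in 14% of trials at 25 per arm and 11% at 30.

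These figures are per dose and unadjusted, as the SAP tests them. They assume the planned rates hold in the analysed patients and that the chi-square is the uncorrected Pearson test. This should be fixed, but it does not undermine the design.

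**What to change.** Keep the two-sided 0.05 test and, before unblinding, name one primary test in SAP 7.1. For example:

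> Each dose is compared with placebo by the two-sided Pearson chi-square test without continuity correction, whatever the expected counts; Fisher's exact test is a sensitivity analysis.

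This suits the planned Miettinen-Nurminen interval, which is also a score method. Then restate the power in SAP 5.1 and protocol 11.1:

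> About 74% power per dose with 25 evaluable patients per arm (about 80% if all 30 are analysed) at two-sided 0.05.

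If the sponsor prefers Fisher, the figures to state are about 60% and 69%.

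The cost is wording only, with no added patients, though the stated power becomes less favourable. The choice of test is a real trade. Pearson's exact level can exceed the nominal 5% at some common rates (at most 6.5% with 25 per arm, 5.5% with 30), although at a 7% rate it is below 5%. Fisher stays well under 5% throughout but gives up 11 to 14 points of power.

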### 5.2 Compliance

IP return and compliance check will be assessed at visit 3, visit 4, visit 5, visit 6 and visit 7. Subjects will be dispensed 3 bottles at each visit. Each bottle contains total 30 tablets and patients will have to take 3 tablets in the morning and 3 tablets in the evening.

Total Compliance will be calculated by using formula:

$$\text{Total Compliance} = \text{Number of actual doses taken} / (\text{Number of expected doses to be taken}) * 100$$

Overall compliance at each visit and during study period will also be calculated by using the above formula as given above. Descriptive statistics by treatment groups will be reported for treatment overall compliance using safety population. A listing will be provided.

### 5.3 Definition and Derived Variables

	JSS Medical Research India Private Limited Data Management		
Title: Statistical Analysis Plan-Module I			
SOP Number: JSS-DM-BIS-01	Current Version Number: 1.0	Previous Version Number: Nil	Document Date: 25MAR2021

### 5.3.1 Baseline

Baseline value is defined as the last non-missing assessment prior to the first study treatment exposure. If the last non-missing assessment is performed on the same date as the first study treatment and time is not available, the assessment will be considered as baseline. In this study, drug is dispensed at visit 2 that is randomization visit which will serve as baseline for efficacy variables.

### 5.3.2 Change from Baseline

Value of change from baseline at any post baseline visit is defined as the difference of the post-baseline value to the baseline value

i.e. Change from baseline ( $\Delta$ ) = post baseline value- baseline value

Percent change from baseline is defined as percentage difference of the post-baseline value to the baseline value, relative to baseline value

i.e. Percent Change from baseline at respective time =

$$\frac{(\text{Post baseline value at respective time} - \text{Baseline value}) \times 100}{\text{Baseline value}}$$

### 5.3.3 End of Treatment

End of treatment value is defined as the last non-missing assessment at the end of study treatment visit i.e. visit 7 (week 12  $\pm$  4 Days). If the subject has not completed the treatment as per protocol, then the last available non-missing value prior to the end of study treatment visit will be used as end of study value and that visit will be considered as early termination visit.

### 5.3.4 Treatment Start Day

Date of first study treatment date is used for treatment start day i.e. visit 2 (day 1) in this study.

### 5.3.5 Treatment End Day

Date of last study treatment date is used for treatment end day until unless the subjects has not prematurely discontinued from the study, then the last date of treatment taken prior to the week 12  $\pm$  4 Days will be used for treatment end day.

### 5.3.6 Duration of Treatment Exposure

	JSS Medical Research India Private Limited Data Management		
Title: Statistical Analysis Plan-Module I			
SOP Number: JSS-DM-BIS-01	Current Version Number: 1.0	Previous Version Number: Nil	Document Date: 25MAR2021

Duration of treatment exposure is defined as the time period in which the subjects was on treatment during the study and will be calculated as follows: number of days between the last dose date and the first dose date plus one i.e.

$$\text{Treatment duration} = \text{date of last dose} - \text{date of first dose} + 1.$$

#### 5.4 Methods for Withdrawals, Missing Data, and Outliers

In case of a patient's withdrawal from the study without any major protocol deviation, its values on subsequent visits will be considered missing.

The last observation carried forward (LOCF) method will be applied to all efficacy measurements (PASI score, IGA mod 2011 score, DLQI score etc.) when at least one post-baseline assessment is available. If all post baseline efficacy values are missing for one efficacy parameter then these missing values will not be imputed and this patient will be removed from the analysis of the corresponding variable, i.e. it might be that the number of patients providing data for one variable is smaller than efficacy population. If withdrawal prior to first post-baseline assessment is considered due to lack of effect of the study drug by the investigator, then the respective patient will be considered as non-responder in PASI and IGA responder analysis, and no change (i.e. post-baseline difference of 0) will be considered for percent or absolute change in PASI, IGA or DLQI parameters.

For missing safety variables, when repeat assessment data is available for the respective visit, then these repeat assessment data will be imputed. E.g. The hematology parameters are not available for Visit 4 for any patient and repeat hematology assessment is done prior to next scheduled visit, then hematology parameters during Visit 4 will be replaced with repeat assessment parameters. However, no values will be replaced if the parameter value is available. For example, if only ALT and AST are not available for a specific visit in biochemistry panel and repeat assessment prior to next visit is done with all liver function tests (ALT, AST, ALP, bilirubin, etc.), then only ALT and AST values will be replaced and other liver function values will not be replaced.

For the efficacy variables (PASI score, IGA mod 2011 score, DLQI score), no observed values will be considered as outliers. For safety parameters like vital signs, lab parameters etc., any value which is out of range will be summarized as observed. However, it will be checked whether it is a normal or abnormal finding and will be

	JSS Medical Research India Private Limited Data Management		
Title: Statistical Analysis Plan-Module I			
SOP Number: JSS-DM-BIS-01	Current Version Number: 1.0	Previous Version Number: Nil	Document Date: 25MAR2021

reported accordingly. For abnormal observed value we further summarized as clinically significance and non- clinically significance.

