In the 13-week repeat dose GLP study in Beagle dogs, doses of 0 (vehicle), 10 mg/kg BID, 30 mg/kg BID, or $60 \rightarrow 50 \rightarrow 40$ mg/kg BID were utilized. Due to observed toxicity, the dosage of the high dose group (Group 4) was reduced from 60 mg/kg BID to 50 mg/kg BID on Day 8 for both sexes, and then further reduced to 40 mg/kg BID from Day 34 after a 5-day dosing holiday from Day 29 to Day 33. It is referred as $60 \rightarrow 50 \rightarrow 40$ mg/kg BID group. There was no mortality in the study. At 10 mg/kg BID and 30 mg/kg BID dose groups, there were no adverse clinical signs or changes in body weight and food consumption. The observed clinical signs at 10 and 30 mg/kg BID dose group were either transient or of lower magnitude. At $60 \rightarrow 50 \rightarrow 40 \text{ mg/kg BID}$ dose, AUR101 related clinical signs included inappetence, prostration, decreased activity, salivation, thinness, tremors, cold to touch, unkempt fur, abnormal stool, vomitus, ocular discharge, ptosis, and/or pale gums during the dosing period, but were resolved at the end of the recovery period. Increases in liver enzymes (AST/ALT) occurred at 30 mg/kg BID as well as at $60 \rightarrow 50 \rightarrow 40$ mg/kg BID. However, the increase at 30 mg/kg BID was mild and reversible and considered non-adverse. The majority of clinical signs noted at $60 \rightarrow 50 \rightarrow 40 \text{ mg/kg}$ BID as well as increase in liver enzymes in this dose group were considered adverse due to the high frequency and/or severity. Consequently, the no-observed-adverse-effect level (NOAEL) in dogs is considered to be 30 mg/kg/dose BID (i.e. 60 mg/kg/day).

In addition to above toxicology studies, the genetic toxicity assessment of AUR101 has also been investigated. Results of an *in vitro* Bacterial Reverse Mutation Test have indicated that AUR101 is non-mutagenic. Similarly, the results of an *in vivo* micronucleus test in Wistar rats and *in vitro* chromosomal aberration test in human peripheral lymphocytes have indicated that AUR101 does not induce clastogenicity.

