7.4 Withdrawal Procedures

If a patient is withdrawn from the study, the primary reason for withdrawal must be recorded in the eCRF. If a patient is withdrawn during the study period after dosing, all safety assessments (e.g. AEs, vitals, ECG, laboratory assessments etc.) according to "End of Treatment" (Week 12 ± 4 days) visit should be performed. Patient will be asked to come 14 ± 2 days after last dose for follow up visit assessments according to study activities **Table 1** If a patient is withdrawn before study drug administration, then safety assessments is not required.

The last date of study drug administration must be documented.

Appropriate follow-up of all withdrawn patients will be performed, as required. If a withdrawn patient does not follow up, then adequate attempts to contact the withdrawn patient must be documented before declaring a patient 'Lost to Follow up'.

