#### 8.5 Laboratory Parameters

The laboratory parameters will include Hematology, Liver function Test, and Renal Function Test samples by visits.

The categorical variables will be analyzed using frequency count and percentage of subjects, and continuous variables will be analyzed using number (n) of non-missing observations, mean, standard deviation, SE and median (IQR) by groups. Any change from baseline in laboratory parameters in terms of normal or abnormal (clinically significant or not significant) findings will also be reported through shift tables for overall data without mentioning the groups. Descriptive statistics (Mean, median, SD, SE and 95% CI) will be presented for change from baseline to the respective visit.

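### As written, SAP 5.4 drops a withdrawn patient's follow-up safety values from the by-visit summaries, and no by-arm laboratory table picks up an unscheduled liver-enzyme peak

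*SAP*

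**What the plan says.** SAP 5.4 covers withdrawals, missing data and outliers for efficacy and safety together. It opens: "In case of a patient's withdrawal from the study without any major protocol deviation, its values on subsequent visits will be considered missing". The efficacy carry-forward rule comes next, then a separate paragraph on safety variables. There, "when repeat assessment data is available for the respective visit, then these repeat assessment data will be imputed", with a limit: "However, no values will be replaced if the parameter value is available". The section also says of safety parameters that "any value which is out of range will be summarized as observed".

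SAP 8.5 sets the laboratory displays: "The laboratory parameters will include Hematology, Liver function Test, and Renal Function Test samples by visits". It plans descriptive statistics by group and visit. Its shift tables (normal, or abnormal and clinically significant or not) are for all patients together, without treatment group. Neither SAP 8.0 nor 8.5 specifies a worst post-baseline value or a multiple-of-ULN display.

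On collection, Protocol 7.4 reads: "If a patient is withdrawn during the study period after dosing, all safety assessments (e.g. AEs, vitals, ECG, laboratory assessments etc.) according to" the End of Treatment visit should be performed. It adds: "Patient will be asked to come 14 ± 2 days after last dose for follow up visit assessments". Protocol Table 1 places laboratory tests, vital signs and a 12-lead ECG at that follow-up visit.

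**The concern.** The protocol asks a withdrawn patient to return for safety tests, and the SAP, taken at its word, then treats those results as missing. A patient who stops for an adverse event will usually have no major protocol deviation, so the sentence would apply. A test repeated between visits because something looked abnormal has no place in a by-visit table when the scheduled values exist. In both cases, whether a value is left out can depend on how the patient is doing. That is the kind of missingness a safety summary should avoid.

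Safety of the two doses is a secondary objective, and Protocol 3.4.1 says that studying two doses will help decide the Phase III dosage. The liver is the natural place to look. In the 13-week dog study, "Increases in liver enzymes (AST/ALT) occurred at 30 mg/kg BID as well as at" the highest dose. The rise at the highest dose was called adverse, as was the ALT and AST rise at the highest dose of the 2-week dog study. Protocol 3.4.1 treats the dog as the more sensitive species and reports a 2.5-fold exposure margin. Phase 1 dosing lasted at most 14 days; this trial doses for 12 weeks.

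**Working it through.** **The plan's own figure.** SAP 5.1 gives 25 per arm for 80% power (7% vs 35%, one-sided 0.05), raised to 30 for 15-20% dropout. A pooled-variance normal approximation at 25 per arm gives 79.9% power. For dropout, 25/(1 − 0.15) = 29.4, rounded up to 30, and 25/(1 − 0.20) = 31.25, rounded up to 32. The figure of 30 thus matches the lower end of the dropout range. This point uses only the 30 per arm and the dropout range.

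**Step 1: which values the withdrawal sentence reaches.**

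| Safety data of a withdrawn patient | Ordered by | Under the sentence as written |
|---|---|---|
| Visits before withdrawal | Protocol Table 1 | Kept |
| Panel at withdrawal (laboratory, ECG, vital signs) | Protocol 7.4 | Kept: not a subsequent visit |
| Follow-up, 14 ± 2 days after last dose (laboratory, ECG, vital signs) | Protocol 7.4, 6.4.4, Table 1 | Missing |

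SAP 5.3.3 does not rescue the last row. It keeps the last value before the end-of-treatment visit as the end-of-study value and does not mention follow-up. For ECG, Table 1 schedules only screening and follow-up, so a withdrawn patient would keep only the withdrawal ECG after dosing.

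**Step 2: where an unscheduled ALT peak goes.** On-treatment laboratory tests fall at Weeks 4, 8 and 12, four weeks apart. Suppose a test between Weeks 4 and 8 shows a peak and both scheduled values exist.

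- By-visit summaries: not included, because a repeat only fills a missing scheduled value.
- Shift tables: pooled over arms, so they cannot show a difference between arms whatever they include.
- Worst-value table: none specified.
- Adverse event tables (SAP 8.1): included only if the investigator judges the value clinically significant (Protocol 10.1, 11.7.3).

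The pooled shift tables also conflict with Protocol 11.7.3 and SAP 8.0, which call for laboratory summaries by treatment.

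**Step 3: how many patients the withdrawal sentence could touch.** Patients = arm size × dropout rate.

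- Per arm: 30 × 0.15 = 4.5; 30 × 0.20 = 6.
- Both AUR101 arms: 60 × 0.15 = 9; 60 × 0.20 = 12.
- All arms: 90 × 0.15 = 13.5; 90 × 0.20 = 18.

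These are upper bounds. They assume that every dropout is a withdrawal without a major deviation and attends follow-up. The number of unscheduled readings left out cannot be computed, since the documents give no rate of such tests or of liver events.

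**Step 4: why visit means are no substitute (illustration on assumed values).** Let one patient in an arm of 30 have ALT at 3 to 5 × ULN and the others 0.6 × ULN. The arm mean moves by (3 − 0.6)/30 = 0.08 to (5 − 0.6)/30 = 0.147 × ULN, even when the value falls on a scheduled visit. This shows dilution, which any by-visit mean has. It does not measure the effect of SAP 5.4.

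**The case against.** The strongest reply is that the withdrawal sentence was meant for efficacy. Its condition, no major protocol deviation, belongs to the efficacy population (SAP 4.3.4); the safety population has no such condition (SAP 4.3.3). The carry-forward rule follows at once, safety has its own paragraph, and out-of-range safety values are to be summarised as observed. That intent is plausible, but the sentence does not say so, and a programmer following it would drop the follow-up values. Even for efficacy it sits badly with Protocol 11.4.1.3, which uses follow-up efficacy data after discontinuation. It also leaves withdrawals with a major deviation without a rule.

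The second reply is that other safety outputs remain. Clinically significant changes are to be reported (SAP 8.0), adverse events are collected to the follow-up visit and tabulated (Protocol 10.1.1, SAP 8.1), and out-of-range results are flagged in listings (Protocol 11.7.3). This stands, and it limits the point to the by-visit and laboratory summaries. The adverse event route still depends on investigator judgement. An event first arising on day 15 or 16, inside the follow-up window, is outside the 14-day treatment-emergent period unless judged related (Protocol 11.7.1).

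Third, the repeat rule also protects signal: a later normal retest cannot overwrite an abnormal scheduled value. That stands too. The rule governs replacement and does not bar repeats from listings or adverse event reporting.

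Fourth, the liver evidence is modest. The rise at 30 mg/kg BID in dogs was mild, reversible and considered non-adverse. Phase 1 found no remarkable effect on liver function. Its two cases, both judged related, were one on placebo (Grade 2) and one on AUR101 (Grade 1).

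**Conclusion.** The point holds for the by-visit laboratory, vital-sign and ECG summaries and for the by-arm laboratory displays. As written, SAP 5.4 sets one protocol-required safety visit to missing for withdrawn patients. SAP 5.4 and 8.5 together leave an unscheduled liver-enzyme peak without any by-arm laboratory summary. At most 4.5-6 of 30 patients per arm could be affected by the first part, on the assumptions in Step 3; the second part cannot be sized from the documents.

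A reader might infer more: that the safety tables as a whole lose the evidence of harm, that the withdrawal panel is discarded, or that a known human liver signal is being hidden. The documents support none of these. Adverse event reporting remains, the withdrawal panel is not a subsequent visit, and the adverse liver findings come from high-dose dogs. The correction is still worth making before analysis, because a stated rule would leave out data already collected, in a way that can depend on outcome.

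**What to change.** In SAP 5.4, restrict the withdrawal sentence to efficacy values at visits not attended, which also fits Protocol 11.4.1.3. Add that all safety values collected from first dose through the follow-up visit are analysed, including early-termination and unscheduled values.

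In SAP 8.5:

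- Present the shift tables by treatment arm.
- Add one by-arm table of the worst post-baseline ALT, AST, ALP and total bilirubin, from scheduled and unscheduled tests, in multiples of ULN. The sponsor should choose the cut-offs in advance; the only one in the documents is the protocol's entry limit of ≥1.5 × ULN.
- Keep the by-visit means on scheduled values, so that extra tests in some patients do not distort them.

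The cost is a wording change, regrouped shift tables and one extra table. No new data, visits or patients are needed.
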